8.4.5 Biomarker Analyses

Not applicable.

8.4.6 Exploratory Biomarker Analyses

Not applicable.

8.4.7 Outcomes Research Analyses

Not applicable.

8.4.8 Immunogenicity Analyses

[REDACTED]

8.5 Interim Analyses

Not applicable.

9. STUDY MANAGEMENT

9.1 Compliance

9.1.1 *Compliance with the Protocol and Protocol Revisions*

The study shall be conducted as described in this approved protocol. All revisions to the protocol must be discussed with, and be prepared by, BMS. The investigator should not implement any deviation or change to the protocol without prior review and documented approval/favorable opinion from the IRB/IEC of an amendment, except where necessary to eliminate an immediate hazard(s) to study subjects.

If a deviation or change to a protocol is implemented to eliminate an immediate hazard(s) prior to obtaining IRB/IEC approval/favorable opinion, as soon as possible the deviation or change will be submitted to:

- IRB/IEC for review and approval/favorable opinion
- BMS
- Regulatory Authority(ies), if required by local regulations

Documentation of approval signed by the chairperson or designee of the IRB(s)/IEC(s) must be sent to BMS.

If an amendment substantially alters the study design or increases the potential risk to the subject: (1) the consent form must be revised and submitted to the IRB(s)/IEC(s) for review and approval/favorable opinion; (2) the revised form must be used to obtain consent from subjects currently enrolled in the study if they are affected by the amendment; and (3) the new form must be used to obtain consent from new subjects prior to enrollment.

If the revision is done via an administrative letter, investigators must inform their IRB(s)/IEC(s).

9.1.2 *Monitoring*

Representatives of BMS must be allowed to visit all study site locations periodically to assess the data quality and study integrity. On site they will review study records and directly compare them with source documents, discuss the conduct of the study with the investigator, and verify that the facilities remain acceptable.

In addition, the study may be evaluated by BMS internal auditors and government inspectors who must be allowed access to CRFs, source documents, other study files, and study facilities. BMS audit reports will be kept confidential.

The investigator must notify BMS promptly of any inspections scheduled by regulatory authorities and promptly forward copies of inspection reports to BMS.

9.1.2.1 *Source Documentation*

The investigator is responsible for ensuring that the source data are accurate, legible, contemporaneous, original and attributable, whether the data are hand-written on paper or entered electronically. If source data are created (first entered), modified, maintained, archived, retrieved, or transmitted electronically via computerized systems (and/or any other kind of electronic devices) as part of regulated clinical trial activities, such systems must be compliant with all applicable laws and regulations governing use of electronic records and/or electronic signatures. Such systems may include, but are not limited to, electronic medical/health records, AE tracking/reporting, protocol required assessments, and/or drug accountability records.

When paper records from such systems are used in place of electronic format to perform regulated activities, such paper records should be certified copies. A certified copy consists of a copy of original information that has been verified, as indicated by a dated signature, as an exact copy having all of the same attributes and information as the original.

9.1.3 *Investigational Site Training*

Bristol-Myers Squibb will provide quality investigational staff training prior to study initiation. Training topics will include but are not limited to: GCP, AE reporting, study details and procedure, electronic CRFs, study documentation, informed consent, and enrollment of WOCBP.

9.2 *Records*

9.2.1 *Records Retention*

The investigator must retain all study records and source documents for the maximum period required by applicable regulations and guidelines, or institution procedures, or for the period specified by BMS, whichever is longer. The investigator must contact BMS prior to destroying any records associated with the study and BMS will notify the investigator when the study records are no longer needed.

If the investigator withdraws from the study (eg, relocation, retirement), the records shall be transferred to a mutually agreed upon designee (eg, another investigator, IRB). Notice of such transfer will be given in writing to BMS.

9.2.2 *Study Drug Records*

It is the responsibility of the investigator to ensure that a current disposition record of study drug (inventoried and dispensed) is maintained at the study site to include the investigational product. Records or logs must comply with applicable regulations and guidelines and should include:

- amount received and placed in storage area
- amount currently in storage area
- label identification number or batch number
- amount dispensed to and returned by each subject, including unique subject identifiers
- amount transferred to another area/site for dispensing or storage
- nonstudy disposition (eg, lost, wasted)
- amount destroyed at study site, if applicable
- amount returned to BMS

- retained samples for bioavailability/bioequivalence, if applicable
- dates and initials of person responsible for Investigational Product dispensing/accountability, as per the Delegation of Authority Form

BMS will provide forms to facilitate inventory control if the investigational site does not have an established system that meets these requirements.

9.2.3 Case Report Forms

An investigator is required to prepare and maintain adequate and accurate case histories designed to record all observations and other data pertinent to the investigation on each individual treated or entered as a control in the investigation. Data that are derived from source documents and reported on the CRF must be consistent with the source documents or the discrepancies must be explained. Additional clinical information may be collected and analyzed in an effort to enhance understanding of product safety. CRFs may be requested for AEs and/or laboratory abnormalities that are reported or identified during the course of the study.

For sites using the BMS electronic data capture tool, electronic CRFs will be prepared for all data collection fields except for fields specific to SAEs and pregnancy, which will be reported on the paper or electronic SAE form and Pregnancy Surveillance form, respectively. Spaces may be left blank only in those circumstances permitted by study-specific CRF completion guidelines provided by BMS.

The confidentiality of records that could identify subjects must be protected, respecting the privacy and confidentiality rules in accordance with the applicable regulatory requirement(s).

The investigator will maintain a signature sheet to document signatures and initials of all persons authorized to make entries and/or corrections on CRFs.

The completed CRF, including any paper or electronic SAE/pregnancy CRFs, must be promptly reviewed, signed, and dated by the investigator or qualified physician who is a subinvestigator and who is delegated this task on the Delegation of Authority Form. For electronic CRFs, review and approval/signature is completed electronically through the BMS electronic data capture tool. The investigator must retain a copy of the CRFs including records of the changes and corrections.

Each individual electronically signing electronic CRFs must meet BMS training requirements and must only access the BMS electronic data capture tool using the unique user account provided by BMS. User accounts are not to be shared or reassigned to other individuals.

9.3 Clinical Study Report and Publications

For this single site protocol, the principal investigator for the site will sign the clinical study report.

The data collected during this study are confidential and proprietary to BMS. Any publications or abstracts arising from this study require approval by BMS prior to publication or presentation and must adhere to BMS's publication requirements as set forth in the approved clinical trial agreement (CTA). All draft publications, including abstracts or detailed summaries of any proposed presentations, must be submitted to BMS at the earliest practicable time for review, but

at any event not less than 30 days prior to submission or presentation unless otherwise set forth in the CTA. BMS shall have the right to delete any confidential or proprietary information contained in any proposed presentation or abstract and may delay publication for up to 60 days for purposes of filing a patent application.

10. GLOSSARY OF TERMS

Term	Definition
Complete Abstinence	
If 1 form of contraception is required, complete abstinence is defined as complete avoidance of heterosexual intercourse and is an acceptable form of contraception for all study drugs. Female subjects must continue to have pregnancy tests. Acceptable alternate methods of highly effective contraception must be discussed in the event that the subject chooses to forego complete abstinence.
 
If 2 forms of contraception are required, complete abstinence is defined as complete avoidance of heterosexual intercourse and is an acceptable form of contraception for all study drugs. Subjects who choose complete abstinence are not required to use a second method of contraception, but female subjects must continue to have pregnancy tests. Acceptable alternate methods of highly effective contraception must be discussed in the event that the subject chooses to forego complete abstinence.
 
Expanded definition Complete abstinence as defined as complete avoidance of heterosexual intercourse is an acceptable form of contraception for all study drugs. This also means that abstinence is the preferred and usual lifestyle of the patient. This does not mean periodic abstinence (eg, calendar, ovulation, symptothermal, profession of abstinence for entry into a clinical trial, postovulation methods) and withdrawal, which are not acceptable methods of contraception. Subjects who choose complete abstinence are not required to use a second method of contraception, but female subjects must continue to have pregnancy tests. Acceptable alternate methods of highly effective contraception must be discussed in the event that the subject chooses to forego complete abstinence.

11. LIST OF ABBREVIATIONS

Term	Definition
AE	adverse event
ALT	alanine aminotransferase
AST	aspartate aminotransferase
AUC	area under the serum concentration-time curve
AUC(INF)	area under the serum concentration-time curve from time zero extrapolated to infinite time
AUC(0-T)	area under the serum concentration-time curve from time zero to time of the last quantifiable concentration
BMI	body mass index
BMS	Bristol-Myers Squibb
CFR	Code of Federal Regulations
CI	confidence interval
CLT	total body clearance
Cmax	maximum observed serum concentration
CRF	case report form, paper or electronic
CTA	clinical trial agreement
DILI	drug induced liver injury
DSM IV	Diagnostic and Statistical Manual of Mental Disorders (4 th Edition)
ECG	electrocardiogram
ECL	electrochemiluminescence
eCRF	electronic case report form
eg	exempli gratia (for example)
FSH	follicle-stimulating hormone
GCP	Good Clinical Practice
HIV	human immunodeficiency virus
HRT	hormone replacement therapy
IB	Investigator Brochure
ICF	informed consent form
ICH	International Conference on Harmonisation

Term	Definition
ie	id est (that is)
IEC	Independent Ethics Committee
IMP	investigational medicinal product
IND	Investigational New Drug
IP	investigational product
IRB	Institutional Review Board
IU	International Unit
IUD	intrauterine device
IV	intravenous
L	liter
mg	milligram
mL	milliliter
mm Hg	millimeters of mercury
ng	nanogram
NHV	normal healthy volunteer
OTC	over the counter
PK	pharmacokinetic(s)
SAE	serious adverse event
TB	tuberculosis
T-HALF	half-life
Tmax	time of maximum observed serum concentration
ULN	upper limit of normal
Vss	volume of distribution at steady state
WOCBP	women of childbearing potential

APPENDIX 1 DIAGNOSTIC CRITERIA FOR DRUGS AND ALCOHOL ABUSE

The following is taken from DSM-IV:

Diagnostic Criteria for Psychoactive Substance Dependence

A maladaptive pattern of substance use, leading to clinically significant impairment or distress as manifested by three (or more) of the following, occurring at any time in the same 12-month period:

1. Tolerance, as defined by either of the following:
 - a) A need for markedly increased amounts of the substance to achieve intoxication or desired effect,
 - b) Markedly diminished effect with continued use of the same amount of the substance.
2. Withdrawal, as manifested by either of the following:
 - a) The characteristic withdrawal syndrome for the substance,
 - b) The same (or closely related) substance is taken to relieve or avoid withdrawal symptoms.
3. The substance is often taken in larger amounts or over a longer period than was intended.
4. There is a persistent desire or unsuccessful efforts to cut down or control substance use.
5. A great deal of time is spent in activities necessary to obtain the substance (eg, visiting multiple doctors or driving long distances), use the substance (eg, chain-smoking) or recover from its effects.
6. Important social, occupational or recreational activities are given up or reduced because of substance use.
7. The substance use is continued despite knowledge of having a persistent or recurring physical or psychological problem that is likely to have been caused or exacerbated by the substance (e.g., current cocaine use despite recognition of cocaine-induced depression, or continued drinking despite recognition that an ulcer was made worse by alcohol consumption).

Criteria for Severity of Psychoactive Substance Dependence:

Mild: Few, if any, symptoms in excess of those required to make the diagnosis, and the symptoms result in no more than mild impairment in occupational functioning or in usual social activities or relationships with others.

Moderate: Symptoms or functional impairment between “mild” and “severe”.

Severe: Many symptoms in excess of those required to make the diagnosis, and the symptoms markedly interfere with occupational functioning or with usual social activities or relationships with others.

In Partial Remission: During the past six months, some use of the substance and some symptoms of dependence.

In Full Remission: During the past six months, either no use of the substance, or use of the substance and no symptoms of dependence.

Diagnostic Criteria for Psychoactive Substance Abuse

- A. maladaptive pattern of psychoactive substance use, leading to clinically significant impairment or distress as manifested by one (or more) of the following, occurring at any time in the same 12-month period:
 - 1. Recurrent substance use resulting in a failure to fulfill major role obligations at work, school, or home (e.g., repeated absences or poor work performance related to substance use; substance-related absences, suspensions, or expulsions from school, neglect of children or household).
 - 2. Recurrent substance use in situations in which it is physically hazardous (eg, driving an automobile or operating a machine when impaired by substance use).
 - 3. Recurrent substance-related legal problems (eg, arrests for substance-related disorderly conduct).
 - 4. Continued substance use despite having persistent or recurrent social or interpersonal problems caused or exacerbated by the effects of the substance (eg, arguments with spouse about consequences of intoxication, physical fights).
- B. The symptoms have never met the criteria for substance dependence for this class of substance

1 BACKGROUND AND RATIONALE

Background:

Renal transplantation is the most effective treatment for adults and pediatric patients of all ages with end stage renal disease. Compared with dialysis, kidney transplantation offers improved medical outcome, cognitive function, social adjustment, and quality of life.^{1,2} Significant unmet medical needs remain in kidney transplantation, among which is the need for new therapies that can reduce the substantial toxicities associated with calcineurin inhibitor-based immunosuppressive regimens.

Study Rationale:

This will be an open-label, randomized, parallel-group, single-dose study to compare the PK of belatacept between 2 drug products manufactured by 2 different processes administered in healthy subjects. Parallel design was selected because the long half-life (T-HALF; approximately 10 days) would make it operationally challenging to washout and retain subjects, and the potential impact of immunogenicity response on PK in a crossover design. Previous studies have shown that there is a trend of higher clearance with increasing body weight.⁴ Belatacept has linear PK from 1 to 20 mg/kg. This study will assess the most clinically applicable dose, 10 mg/kg, which is the highest approved dose. Belatacept has been given as single doses to normal healthy volunteers (NHVs) and shown to be safe and well tolerated.⁵ There have been no deaths or serious adverse events (SAEs), and no subjects have discontinued from a study due to adverse events (AEs) in the pooled NHV population. A study in healthy volunteers is considered to be more sensitive in evaluating the product similarity because it is likely to produce less PK

variability compared with that in patients with potentially confounding factors such as underlying and/or concomitant disease and concomitant medications.⁶

Research Hypothesis:

The PK of belatacept manufactured by Process E (Process E belatacept) and by Process C (Process C belatacept) are comparable in healthy subjects, based on exposure as measured by area under the serum concentration-time curve (AUC) from time zero extrapolated to infinite time (AUC[INF]) and maximum observed serum concentration (C_{max}).

Schedule of Analyses:

Final analysis will be performed following database lock according to agreed-upon reporting milestone(s), typically after all subjects have completed the study.

Exclusions of Site 2 Data Due to Major Protocol Deviations:

Prior to protocol amendment 02 (dated September 27, 2016), 146 subjects were dosed at 3 clinic sites: 60 at Site 1 (PPD), 30 at Site 2 (SNBL), and 56 at Site 3 (MRA). Audit and monitoring visits revealed major protocol deviations at Site 2 including but not limited to inclusion/exclusion criteria deviations, not providing HIPAA consent at screening visit, incomplete source documentation, failure to obtain laboratory tests within the pre-specified windows, failure to obtain protocol-specified laboratory tests, and incorrect handling of blood samples. Due to the number and significance of these deviations affecting the data of all subjects at Site 2, the 30 dosed subjects were not considered eligible for the analysis of the study endpoints.

Removing the data from the 30 dosed subjects at Site 2 from the analysis without replacing it would result in a total of 116 dosed subjects and under-power the study (approximately 74% power, assuming a true difference of 11%).

The protocol amendment 02 (dated September 27, 2016) was written to replace those 30 dosed subjects at Site 2 with 30 new subjects at Site 1 and Site 3, in order to maintain sufficient power. Randomization of the 30 new subjects was stratified by weight categories in the same way as for the originally planned subjects.

The 30 dosed subjects at Site 2 will not be included in the analysis and 30 replacement subjects dosed at Site 1 and Site 3 will be included in the analysis. A total of 176 subjects will be dosed including the originally planned 146 subjects and the 30 replacement subjects.

In addition, the data from the subjects who were enrolled at Site 2 will only be presented in the listings and be excluded from any summaries or statistical analyses.

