4.2 Safety Endpoints

Safety endpoints include the occurrence of AEs, SAEs, and AEs leading to discontinuation; results of clinical laboratory tests, vital sign measurements, ECG findings, and physical examinations; and marked abnormalities in clinical laboratory test results.

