6.3 Populations for Analyses

The exclusion of the subjects from Site 2 due to major protocol deviations is described in the footer of planned outputs in the Data Presentation Plan (DPP) as appropriate.

- The Enrolled Population includes all subjects who sign an ICF.
- The Randomized Population is a subset of the Enrolled Population including only subjects who were randomly assigned to a treatment. When using the Randomized Population, subjects will be presented in the treatment group they were randomly assigned to, even when the treatment they received was different.
- The Treated Population is a subset of the Enrolled Population including only subjects who received a dose of study medication. All analyses using the Treated Population will be presented by randomized treatment group, except in cases where information was available which indicated that a subject received a different treatment for the entire course of their participation in the study. In this case, the safety data and PK data for those subjects will be presented by the treatment actually received.

- The PK Population is a subset of the Treated Population. The PK population includes all treated subjects who had any available concentration-time data and did not have any protocol deviations which were determined to affect PK parameters.
- The Evaluable PK Population is a subset of the PK Population. The Evaluable PK Population includes all subjects who have adequate PK profiles. All available derived PK parameter values will be included in the PK data set and reported, but only subjects with adequate PK profiles will be included in the summary statistics and statistical analysis.
- The Immunogenicity Analysis Population: All treated subjects with at least 1 post-baseline immunogenicity result reported will be included in immunogenicity analysis.

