7.1 General Methods

The data from the subjects who were enrolled at Site 2 will not be included in any summaries or statistical analyses. These data will only be presented in the listings. Details of the data presentation are specified in the DPP. The data from the 30 replacement subjects along with the data from the initial 116 subjects who were enrolled and dosed at the other sites will be used for analyses.

All data recorded on case report forms will be listed by subject. Descriptive summaries will be presented for continuous variables using number of subjects (N), mean, standard deviation (SD), median, minimum and maximum. Geometric mean and coefficient of variation (CV%) will also be presented for sample serum concentration-time data and PK parameters. Descriptive summaries for categorical variables will utilize counts and percentages.

For all treatment comparisons, a linear fixed effect model with treatment as a fixed effect will be fitted to the log-transformed PK parameters C_{max}, AUC(0-T) and AUC(INF) for use in estimation of effects and construction of CIs. Point estimates and 90% CIs for differences on the log-scale will be exponentiated to obtain estimates for ratios of geometric means and respective 90% confidence intervals on the original scale. The SAS procedure (PROC MIXED) will be used to derive all inter-subject variances, and for the estimation of test to reference ratios and respective confidence intervals.

Adverse events and medical history will be coded according to the most recent Medical Dictionary for Regulatory Activities (MedDRA) version. Previous and concomitant medications will be coded using the BMS Drug Dictionary.

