7.6 Safety

Analysis of all safety data will follow the BMS guideline of analysis of safety data⁷.

The evaluation of safety is based on clinical AEs, vital signs, ECG results, clinical laboratory results, and physical examination findings reported during the study. Unless otherwise specified, all safety presentations will utilize the treated population as described in [Section 6.3](#).

All recorded AEs will be listed and tabulated by system organ class (SOC), preferred term (PT), treatment and overall. Any physical examination findings will be listed. ECG, vital signs and clinical laboratory test results and corresponding change from baseline values will be listed and

summarized by treatment and visit. Values for ECG, vital signs and clinical laboratory test results outside the pre-specified criteria will also be listed and summarized. Electrocardiogram readings will be evaluated by the investigator and abnormalities, if present, will be listed.

Where appropriate, baseline is defined as the last non-missing result with a collection date-time less than the date-time of the first active dose of study medication, for laboratory results, vital signs, and ECG results.

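### The SAP's Site 2 exclusion leaves 30 of 176 dosed subjects (17.0%) out of the AE incidence tables, and SAP 7.6.2 and 7.6.3 do not refer to that rule

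*SAP*

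**What the plan says.** **The exclusion.** Protocol 8.4 removes the 30 Site 2 subjects from the primary analysis and leaves the rest of their handling to the SAP. SAP section 1 goes further: data from subjects enrolled "at Site 2 will only be presented in the listings and be excluded from any summaries or statistical analyses". It also states that "the 30 dosed subjects were not considered eligible for the analysis of the study endpoints". SAP 7.1 repeats the rule: "The data from the subjects who were enrolled at Site 2 will not be included in any summaries or statistical analyses". The same paragraph of 7.1 names who is analysed: the 116 subjects initially dosed at the other sites plus the 30 replacements.

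**The reason.** SAP section 1 gives a non-exhaustive list of deviations that starts with "inclusion/exclusion criteria deviations, not providing HIPAA consent at screening visit, incomplete source documentation". It goes on to missed or out-of-window laboratory tests and mishandled blood samples, and says that the data of every Site 2 subject were affected.

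**The safety sections.** SAP 4.2 makes adverse events endpoints of the study: "Safety endpoints include the occurrence of AEs, SAEs, and AEs leading to discontinuation". SAP 3.2 makes the safety of both processes a secondary objective. SAP 7.6 sets the default population: "Unless otherwise specified, all safety presentations will utilize the treated population". SAP 6.3 defines that population without mentioning Site 2: "The Treated Population is a subset of the Enrolled Population including only subjects who received a dose of study medication". Ahead of its definitions, 6.3 does carry one sentence on the subject: "The exclusion of the subjects from Site 2 due to major protocol deviations is described in the footer of planned outputs", with the Data Presentation Plan (DPP) as the place to look. SAP 7.6.2 puts the SAEs of all enrolled subjects into the summary. SAP 7.6.3 takes everyone given study treatment as the denominator for AE proportions. Neither mentions Site 2.

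**The concern.** The reason for removing Site 2 from the PK comparison does not carry over automatically to safety. A concentration from a badly handled sample can bias a geometric mean ratio. An adverse event in a subject who was dosed is still an event after exposure to belatacept. Under the SAP rule these subjects appear in listings only, so a reader of the study report would find no AE or SAE incidence by treatment that covers everyone exposed.

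There is also a drafting problem. A programmer who follows 7.6.2 and the 6.3 definitions as written would include Site 2. One who follows 7.1 would leave it out. The intent is fairly clear, but the sections that specify the safety tables do not state it.

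The primary PK conclusion is not at stake.

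**Working it through.** **1. The plan's own counts (SAP section 1).** Dosed before Amendment 02: 60 at Site 1, 30 at Site 2, 56 at Site 3. Replacements at Sites 1 and 3: 30.

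- 60 + 30 + 56 = 146 dosed originally
- 146 − 30 = 116 outside Site 2
- 116 + 30 = 146 used for analyses
- 146 + 30 = 176 dosed in total

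All agree with the SAP.

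**2. Share missing from the AE tables.** 30/176 = 0.1705, or 17.0% of dosed subjects.

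**3. Share missing from the SAE summary.** SAP 7.6.2 is defined on enrolled subjects, meaning those who signed consent. Neither document says how many enrolled at Site 2, so no figure can be given.

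**4. What the omission could hide.** For an assumed true event rate p, the chance that an event type occurs among the 30 and in none of the other 146 is (1 − p)^146 × [1 − (1 − p)^30].

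| Assumed p | Chance |
|---|---|
| 0.5% | 6.7% |
| 1% | 6.0% |
| 2% | 2.4% |
| 5% | 0.04% |

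The maximum is 6.9%, at p of about 0.62%. Such an event would be absent from the tables but still listed.

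**5. Precision when no event is seen.** The one-sided 95% upper bound is 1 − 0.05^(1/n).

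| n | Upper bound |
|---|---|
| 146 | 2.03% |
| 176 | 1.69% |
| 73 per arm | 4.02% |
| 88 per arm | 3.35% |

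The per-arm figures assume that Site 2 split evenly between treatments; the split is not given.

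**6. What adding Site 2 could cost.** If Site 2 recorded only a fraction c of its events, all-treated incidence is multiplied by (146 + 30c)/176. The values of c are assumed.

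| c | Factor | Relative understatement | A true 10% is shown as |
|---|---|---|---|
| 0.75 | 0.957 | 4.3% | 9.6% |
| 0.50 | 0.915 | 8.5% | 9.1% |
| 0.25 | 0.872 | 12.8% | 8.7% |

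**7. The texts side by side.**

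- *7.1 against 7.6.2:* 7.1 bars Site 2 from every summary, while 7.6.2 summarizes SAEs for all enrolled subjects. Read literally, both cannot hold. A benign reading exists: protocol 6.1.1 collects SAEs from consent onward, so the enrolled wording may be meant only to bring in SAEs before dosing.
- *7.1 against 7.6.3:* the 7.6.3 denominator is 176 if read alone and 146 if read under 7.1. It carries no cross-reference.
- *7.1 against 6.3:* the opening sentence of 6.3 acknowledges the exclusion but changes neither the Enrolled nor the Treated definition.

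**The case against.** The case for leaving the plan alone is substantial.

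- The rule is explicit. SAP 7.1 stands at the head of the statistical section, bars Site 2 from all summaries and names the 116 + 30 subjects to be used. The opening words of SAP 7.6 leave room for such a rule, and 6.3 announces it.
- Protocol 8.4 hands the matter to the SAP, and SAP 7.2 says that changes from protocol-specified analyses will be defined there.
- Incomplete source documentation across a whole site is a good reason not to pool its AE data.
- Site 2 events, and any deaths under SAP 7.6.1, remain listed.
- The gain is small: the zero-event bound moves from 2.03% to 1.69%. SAP section 1 reports no deaths or SAEs in pooled healthy-volunteer data.

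All of this stands, and it is why the planned tables should stay. It does not supply an incidence table for all exposed subjects, and it does not remove the literal conflict in 7.6.2.

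A reader might infer three stronger points that the documents do not support.

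- *That the SAP departs from the protocol.* Protocol 8.4.3 tabulates AEs and SAEs without a site exception, but it sits under 8.4, which delegates the handling of Site 2.
- *That the SAP builds proportions with Site 2 in the numerator or the denominator but not both.* No section prescribes this, and 7.1 fixes one analysis set of 146. It would take a programming error against 7.1.
- *That 17.0% is also the share missing from the SAE summary.* That share is unknown.

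**Conclusion.** The point holds as a minor one, with medium confidence. Following the stated rule, the AE incidence tables for a secondary objective describe 146 of 176 dosed subjects. The exclusion is permitted and defensible, no data are lost from the report, and PK is unaffected. What is missing is an all-exposed safety table to set beside the planned one, and wording in 7.6.2, 7.6.3 and the 6.3 definitions that points to the 7.1 rule.

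The 17.0% rests only on the SAP's counts. The event rates, the capture fractions and the even split of Site 2 by arm are assumptions. Confidence is medium because the DPP, to which 6.3 and 7.1 defer for presentation, is not among the documents and may settle part of the wording.

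**What to change.** 1. Keep the planned AE and SAE tables without Site 2.
2. Add supplementary AE and SAE incidence tables by treatment on all 176 treated subjects. Footnote the Site 2 deviations (eligibility, HIPAA consent, incomplete source documentation, missed or out-of-window laboratory tests, sample handling) and possible under-capture of AEs.
3. Add a cross-reference to the Site 2 rule of SAP 7.1 in 7.6.2, in 7.6.3, and in the Enrolled and Treated definitions of 6.3. In 7.6.2, say whether the enrolled wording is meant only to bring in SAEs before dosing.

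The exclusion clause in 7.1 needs no change, and PK stays on the 146 subjects outside Site 2.

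The cost is a short reference in three sections and one extra set of tables from data already going into the listings. Nothing planned is removed. Because under-capture at Site 2 would pull the all-treated incidence down, the added tables should be read beside the planned ones and not replace them.
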